4.0 TREATMENT PLAN

4.1 OVERVIEW

The eligible study population will consist of adult patients with histologically confirmed, measurable, unresectable or metastatic angiosarcoma who have progressive disease after prior treatment with ifosfamide, doxorubicin or a taxane. Patients will be treated with daily oral regorafenib (160 mg) for 3 weeks on followed by 1 week off (1 cycle = 4 weeks). Patients will continue treatment until disease progression or withdrawal due to unacceptable toxicity. Once off-treatment, patients will be followed for overall survival up to 5 years. An optimal two-stage Simon design will be employed. The first stage will include 12 patients. If > 3 patients achieve a PFS > 4 months, an additional 19 patients will be enrolled for a total of 31 patients.

4.2 TREATMENT ADMINISTRATION

Regorafenib will be administered orally at a dose of 160 mg regorafenib for 3 weeks on followed by 1 week off. One cycle is 4 weeks (28 days). Patients will be instructed to take 4 40mg regorafenib tables every morning with approximately 8 fluid ounces (240 mL) of water after a low-fat (< 30% fat) breakfast. Patients will be given examples of low fat breakfasts, such as:

- Two slices of white toast with 1 tablespoon of low-fat margarine and 1 tablespoon of jelly and 8 ounces (240 mL) of skim milk (approximately 319 calories and 8.2 g of fat).
- One cup of cereal (i.e. Special K), 8 ounces (240 mL) of skim milk, one piece of toast with jam (no butter or marmalade), apple juice, and one cup of coffee or tea (2 g fat, 17 g protein, 93 g of carbohydrate, 520 calories).

4.3 DOSE MODIFICATION & MANAGEMENT OF TOXICITY

4.3.1 Dose Reductions/Re-escalations

The starting dose of regorafenib is 160 mg once daily. Study medication will be administered on a schedule of 3 weeks on followed by 1 week off (1 cycle = 4 weeks). Doses will be delayed or reduced for clinically significant hematologic and non-hematologic toxicities that are related to protocol therapy according to the guidelines shown in Table 1 below. Dose modifications will follow predefined dose levels. Dose adjustments for hematologic toxicity are based on the blood counts obtained in preparation for the day of treatment.

NOTE: In some cases, dose re-escalation may be permitted at the discretion of the treating investigator. Please refer to the tables below for details regarding when this is acceptable and under what conditions.

Table 1: Pre-defined dose modification levels

Dose Level	Dose	# of Regorafenib Tablets
Dose level 0 ¹	160 mg PO qd	4 40mg tablets
Dose level - 1	120 mg PO qd	3 40-mg tablets
Dose level - 2	80 mg PO qd	2 40-mg tablets

¹Standard starting dose

If a subject experiences more than one toxicity, dose reduction should be according to the toxicity with the highest grade unless that toxicity is unequivocally deemed not to be causally related to study treatment. In such cases, the investigator may dose reduce according to the toxicity deemed most causally related to study treatment.

Table 2 below outlines dose adjustments for toxicities related to study drug *except* hand-foot skin reaction, hypertension and liver function test abnormalities.

Table 2: Dose Modifications for Toxicities*

Toxicity Grade ^a	Dose Interruption	Dose Modification ^b	Dose for Subsequent Cycles
Grade 0-2	None – Treat on time	No change	No change
Grade 3	Delay until ≤ Grade 2 ^c	Reduce by 1 dose level	If toxicity remains < Grade 2, dose re-escalation can be considered at the discretion of the treating investigator. If dose is re-escalated and toxicity (≥ Grade 3) recurs, institute permanent dose reduction.
Grade 4	Delay until ≤ Grade 2 ^c	Reduce by 1 dose level. Permanent discontinuation	

		can be considered at treating investigator's discretion.	

a. According to the National Cancer Institute – Common Terminology Criteria for Adverse Events, version 4.0 (NCI CTCAE v 4.0)
 
b. Excludes alopecia, non-refractory nausea/vomiting, non-refractory hypersensitivity and nonclinical and asymptomatic laboratory abnormalities.
 
c. If no recovery after a 4 week delay*, treatment should be permanently discontinued unless subject is deriving clinical benefit.
 
* Dose modifications are for toxicities except hand-foot-skin reaction, hypertension, and ALT/AST/bilirubin abnormalities. Refer to the tables below for management of these.
			

In addition to these recommended dose modifications, subjects who develop diarrhea, mucositis, anorexia or other events predisposing to fluid loss or inadequate fluid intake should be carefully monitored and rehydrated as clinically necessary. This is in order to minimize the risk of postural hypotension and renal failure.

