Grade 1: Prehypertension (systolic BP 120 - 139 mmHg or diastolic BP 80 - 89 mmHg)	None	
 • Continue regorafenib • Consider increasing blood pressure (BP) monitoring
Grade 2: Systolic BP 140 - 159 mmHg or diastolic BP 90 - 99 mmHg OR Symptomatic increase by > 20 mmHg (diastolic) if previously within normal limits	
 • Treat with the aim to achieve diastolic BP ≤ 90 mm Hg: • If BP previously within normal limits, start anti-hypertensive monotherapy • If patient already on anti-hypertensive medication, titrate up the dose. 	
 • Continue regorafenib • If symptomatic, hold regorafenib until symptoms resolve AND diastolic BP ≤ 90 mm Hg^a. When regorafenib is restarted, continue at the same dose level.
Grade 3: Systolic BP ≥ 160 mmHg or diastolic BP ≥ 100 mmHg OR More than one drug or more intensive therapy than previously used indicated	Treat with the aim to achieve diastolic BP ≤ 90 mm Hg: Start anti-hypertensive medication AND/OR Increase current anti-hypertensive medication AND/OR Add additional anti-hypertensive medications.	
 • Hold regorafenib until diastolic BP ≤ 90 mm Hg, and if symptomatic, until symptoms resolve.^a • When regorafenib is restarted, continue at the same dose level. • If BP is not controlled with the addition of new or more intensive therapy, reduce by 1 dose level.^b • If Grade 3 hypertension recurs despite dose reduction and antihypertensive therapy, reduce another dose level.^c
Grade 4: Life-threatening consequences (eg, malignant hypertension, transient or permanent neurologic deficit, hypertensive crisis)	Per institutional guidelines	Discontinue therapy
a. Patients requiring a delay of > 4 weeks should go off protocol therapy b. If BP remains controlled for at least one cycle, dose re-escalation permitted per investigator's discretion. c. Patients requiring >2 dose reductions should go off protocol therapy.		

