5.0 STUDY PROCEDURES

Table 7: Study Visit Parameters

	Baseline (-28days)	On Treatment								Off Treatment	Follow-Up ⁱ	
	Screening ^j	Cycle 1 ^{l, n}				Cycle 2 ^{g, l, n}				Cycle 3+ g, l, n	End of study treatment	
Week	0	1	2	3	4	5	6	7	8	9+		
Regorafenib 160 mg ^e		On			Off	On			Off	Continue ^e		
Informed consent	X											
Medical history ^h	X											
Physical examination	X	X				X				X	X	
Vital signs ^a	X	X	X	X	X	X	X	X	X	X	X	
CBC/Diff	X	X				X				X	X	
PT/INR ^b	X	X ^b				X ^b				X ^b	X ^b	
Clinical chemistry ^c	X	X		X		X		X		X ^c	X	
Pregnancy test ^f	X											
Urine Protein/Creatinine Ratio (UPC)	X											
ECOG PS	X	X				X				X	X	
Disease Measurements ^d	X ^d									X ^d	X ^d	
Study medication dispensing & pill diary collection		X				X				X		
Tolerability/AE reporting	X	X	X	X	X	X				X	X	
Adverse Event Self- Report Survey (AESRS)		X ^k				X				X		
Concomitant medications	X	X				X				X	X	
Phone call ^{m, i}			X ^m	X ^m	X ^m							X ⁱ

- a- Vital signs to include height (height is recorded at screen visit only), weight, blood pressure, pulse, temperature. **Blood pressure should be monitored weekly for the first six weeks of study treatment. A patient blood pressure log will be maintained to aid in monitoring (See Appendices). Patients will record blood pressure at home during the weeks they are not coming to the clinic for exams.**
- b- PT/INR should be closely monitored on day 1 of each cycle.
- c- Electrolytes, calcium, magnesium, BUN, serum creatinine, total bilirubin, AST, ALT, alk phos, albumin, amylase, lipase. Should be done every 2 weeks during Cycles 1 and 2; if no abnormalities are seen, may be done on day 1 only of subsequent cycles. Mid-cycle labs may be performed at a local laboratory if needed to accommodate patient travel logistics..
- d **Imaging should be done as clinically indicated** (i.e. CT, MRI and visual measurements), which satisfy RECIST v 1.1 to evaluate disease (such as in extremity, head and neck). Imaging studies will be done at baseline (within 4 weeks (28 days) before the first dose) and repeated after every 2 cycles of treatment (prior to each odd cycle) for tumor response evaluation.
- ePatients will receive regorafenib daily x 3 weeks followed by 1 week off (1 cycle = 4 weeks).
- f- Women of child-bearing potential must have a negative serum pregnancy test within 7 days prior to registration.

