- g- Assessments including physical examination, vital signs, ECOG PS, clinical chemistry, CBC/Diff and PT/INR should immediately precede initiation of the next cycle of therapy. Clinically indicated scans should be performed during the off week immediately preceding initiation of odd numbered cycles.
- h- Medical history findings (i.e. previous diagnoses, diseases or surgeries) will be collected, including those not pertaining to the study indication, beginning before registration, that are considered relevant to the study.
- i- Once off treatment, patients will be followed approximately every 6 months by phone for survival endpoints. Follow-up will continue up to 5 years.
- j- Screening assessments must be completed within 15 days prior to registration, unless otherwise specified. Screening assessments may be used for C1D1 assessments if completed \leq 15 days before study drug initiation.
- k- Adverse Event Self-Report Survey (AESRS) should be disseminated to each patient on day 1 of cycle 1, but no data is collected.
- l- Unless otherwise noted, on-therapy windows for testing will be as follows: imaging scans should be completed within +/- 1 week of the target time point, and labs and physical examination within +/- 3 days of the target time point .
- m- Subjects will be instructed to follow-up weekly with the study team IF they are experiencing any side effects.
- n- Day 1 of each cycle should be every 28 days. In the event that this day falls on a holiday or other such event, study team should use +/- 3 day window to complete pre-treatment procedures, and dispense protocol agents to patients with instructions to commence treatment on day 1. Any missed doses will not be made up and should be skipped to maintain a 28-day cycle.

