6.3 SECONDARY ENDPOINT ASSESSMENT

The progression-free rate (PFR) at 3 and 6 months will be defined as the number of patients with progression absent at these timepoints divided by the total number of study patients. Median PFS (defined as the duration of time from start of treatment until time of progression or death, whichever occurs first) will be estimated as a secondary endpoint. Overall survival will be defined as the time from start of treatment until death by any cause. Response rate (by RECIST v 1.1) will be calculated using the definitions above. The rate and duration of tumor control will be defined as the number of CR+PR+SD responses. Patients must complete at least 2 cycles of study treatment to be considered evaluable for efficacy endpoints.

To evaluate the safety and tolerability of regorafenib, all subjects who receive at least one dose of study treatment will be considered evaluable for the safety analysis. Safety variables will include the following: AEs, laboratory changes (complete blood counts, electrolytes, chemistry, and coagulation), changes in vital signs (blood pressure, heart rate, respiratory rate, and temperature) and results of clinically indicated studies outside study guidance, such as ECG or chest x-ray images, as produced at the investigator’s discretion. All AEs whether considered drug-related or not, will be reported with a diagnosis, start/stop dates, action taken, whether treatment

was discontinued, any corrective measures taken, outcome, and other possible causes. For all events, the relationship to treatment and the intensity of the event will be determined by the investigator. All observations pertinent to the safety of the study treatment will be recorded and included in the final report. This trial will use the NCI CTCAE v 4.0 criteria for assessment of toxicity and SAE reporting with regard to toxicity grade.

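### After the first dose no blood count is scheduled in the on-drug weeks, so the hematologic safety data will describe almost only off-drug values

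*Combined protocol and SAP*

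**What the plan says.** **Regimen.** Section 4.1: "Patients will be treated with daily oral regorafenib (160 mg) for 3 weeks on followed by 1 week off".

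**Blood counts.** The CBC/Diff row of Table 7 (Section 5.0) is marked at screening, week 1, week 5, the single column for cycle 3 onward, and end of treatment. Footnote g adds that "CBC/Diff and PT/INR should immediately precede initiation of the next cycle of therapy". Footnote l gives laboratory tests a window of 3 days either side.

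**Chemistry.** The row is marked at weeks 1, 3, 5 and 7. Footnote c: "Should be done every 2 weeks during Cycles 1 and 2". Mid-cycle samples may go to a local laboratory, and from cycle 3 testing may fall back to day 1 only.

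**Dose adjustment.** Section 4.3.1: "Dose adjustments for hematologic toxicity are based on the blood counts obtained in preparation for the day of treatment". Table 2, in the same section, delays dosing for Grade 3 or 4 toxicity and does not say when in the cycle the grade is determined. On later cycles it adds: "If toxicity remains < Grade 2, dose re-escalation can be considered at the discretion of the treating investigator".

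**Blood pressure.** Footnote a: "Blood pressure should be monitored weekly for the first six weeks of study treatment". Vital signs are marked in each of weeks 1-8 and then once for cycle 3 onward. Table 5 footnote b (Section 4.3.3): "If BP remains controlled for at least one cycle, dose re-escalation permitted".

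**Use of the data.** Safety is a secondary objective (2.2.6). Section 6.3 names as safety variables "laboratory changes (complete blood counts, electrolytes, chemistry, and coagulation" among others, and Section 9.4 plans descriptive summaries of laboratory values, including mean change from baseline.

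**The concern.** A safety summary describes the times at which samples were taken. If all routine counts come at the end of the rest week, the tables will show how patients look before restarting the drug, not while taking it. A fall in counts that arises on drug, causes no symptoms and resolves by the next cycle leaves no trace, and the reported hematologic toxicity is then too low. Chemistry does not have this gap in cycles 1 and 2.

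There is also a wording problem. On a regimen with 21 consecutive dosing days, the treatment day that governs hematologic dose adjustment could mean any of those days or only day 1 of a cycle. Table 2 reads as if a Grade 3 or 4 finding counts whenever it is found. Sites that obtain an unscheduled mid-cycle count could act on it differently, which would add site-to-site variation to both dose exposure and toxicity data.

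**Working it through.** The plan states no figure for this point, so the check is a count of the Table 7 marks and of drug-free days.

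**1. Drug-free days before a pre-cycle count.** The last dose of cycle 1 is on day 21, and the next cycle starts on day 29. Full drug-free days before the sample = (sample day - 1) - 21.
- Target, day 29 before dosing: 28 - 21 = 7.
- Early edge of the window, day 26: 25 - 21 = 4.
- Late edge, day 32: this would follow three doses of the new cycle, but footnote g requires the sample before the cycle starts.

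**2. Scheduled mid-cycle assessments in cycles 1 and 2** (marks outside weeks 1 and 5; 2 x 21 = 42 dosing days).

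| Assessment | Mid-cycle weeks marked | Number |
|---|---|---|
| CBC/Diff | none | 0 |
| Clinical chemistry | 3, 7 | 2 |
| Vital signs, including blood pressure | 2, 3, 4, 6, 7, 8 | 6 |
| AE reporting | 2, 3, 4 | 3 |

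Week 3 is days 15-21 and week 7 is days 43-49. Both lie inside a dosing block, so the chemistry draws are on drug.

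**3. The remaining counts.** The week 1 count is a pre-treatment value; footnote j allows a screening sample to serve for it. The end-of-treatment count has no fixed place in the cycle and may be on drug. From cycle 3 the counts are again pre-cycle.

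**4. Size of the under-ascertainment.** Let p be the true proportion of patients with an on-drug Grade 3-4 cytopenia. Let r be the fraction of them who recover by the pre-cycle count with neither symptoms nor an unscheduled sample. Recorded proportion = p x (1 - r). The documents give neither p nor r, so the recorded figure could lie anywhere from 0 (r = 1) to p (r = 0). No narrower range can be defended.

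**5. Section 4.3.1 beside Table 2.** The sentence ties hematologic adjustment to a count taken ahead of a treatment day. Table 2's interruption column depends on grade alone. Footnote b, which excludes asymptomatic laboratory abnormalities, is attached to the dose-modification column and not to the interruption column. The text does not say how the three combine for a Grade 3 count found, for example, on day 15.

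**6. Blood pressure from cycle 3.** Footnote g places vital signs before the cycle. The Appendix III log has rows for weeks 1-6 only, but the home-recording sentence in footnote a has no end date. It is therefore unclear which readings support the re-escalation condition in Table 5 footnote b.

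**The case against.** A reader might infer from the schedule that dose reduction, re-escalation and reported toxicity all rest on recovered values. The documents do not support that.
- In cycles 1 and 2, blood pressure and chemistry are measured on drug. AEs are collected weekly in cycle 1 and recorded with start and stop dates, and patients with side effects are told to contact the team weekly (footnote m).
- Hand-foot skin reaction, hypertension and liver toxicity have their own rules (Tables 4-6), which are not tied to day-1 values.
- That counts have recovered by day 29 is itself an inference; no recovery data are given.

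The dosing consequence is also limited. Section 4.3.1 confines dose changes to clinically significant toxicity, and Table 2 footnote b excludes asymptomatic laboratory abnormalities from dose modification. Section 7.1 leaves monitoring after a dose change to local standard of care, so it is delegated and not absent. The treatment day can reasonably be read as day 1 of a cycle, given footnotes g and n. The wording is therefore loose, but an outright contradiction is not shown.

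The leading grade 3+ events that Section 1.3.2 quotes from the two phase III trials include no cytopenia. Its hypertension rates of 7% and 48.5% would be 0.07 x 31 = 2.2 and 0.485 x 31 = 15.0 patients. Those figures would count patients reaching Grade 3, not the smaller group dose-reduced from cycle 3 and then considered for re-escalation.

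All of this stands, and it narrows the point. It does not close the gap in the counts. Start and stop dates, symptom-triggered contact and the recording of unscheduled tests cannot capture a cytopenia that is neither felt nor sampled.

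**Conclusion.** The point holds for scheduled blood counts. Every pre-cycle count after the first dose follows 4 to 7 drug-free days, and none is scheduled on drug in the 42 dosing days of cycles 1 and 2. The hematologic part of the safety objective would therefore rest almost entirely on off-drug values, apart from end-of-treatment and unscheduled counts. The direction of any error is toward under-reporting, but its size cannot be estimated from the documents and may be small. This rests on Table 7 being followed as marked, with footnote g limiting the late side of the window.

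The undefined treatment day in Section 4.3.1 and its unclear fit with Table 2 need reconciling. Blood pressure from cycle 3 is a smaller matter of the same kind. The primary endpoint and the two-stage decision rule are not affected. The change is worth making because the objective is stated, the variable is named, and the draws already exist.

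**What to change.** 1. For safety ascertainment, mark CBC/Diff in Table 7 at weeks 3 and 7, on the chemistry draws already scheduled there. In safety reporting, state when in the cycle each count was taken. Cost: at most 2 x 31 = 62 extra tests, fewer if the trial stops at stage 1 (2 x 12 = 24) or patients leave early, and no new visits. Reported hematologic toxicity may rise somewhat. Counts from cycle 3 stay pre-cycle, which the timing statement would make visible.

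2. Define the treatment day in Section 4.3.1, and reconcile that sentence with Table 2 (including footnote b and the re-escalation condition) and with Table 7.

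3. Reconcile Table 5 footnote b, Table 7 footnote a and the Appendix III log, so that it is clear which readings are meant.

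Items 2 and 3 ask only that the passages agree; the sponsor decides which clinical rule applies. All three fit in one short protocol amendment.

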4.3.2 Management and Dose Modifications for HFSR

Table 3: Grading for Hand-Foot-Skin Reaction

	Grade 1	Grade 2	Grade 3
CTCAE v 4.0: Palmar-plantar erythrodysesthesia syndrome^a	Minimal skin changes or dermatitis (e.g., erythema, edema, or hyperkeratosis) without pain	Skin changes (e.g., peeling, blisters bleeding, edema, or hyperkeratosis) with pain	Severe skin changes (e.g., peeling, blisters, bleeding, edema, or hyperkeratosis) with pain
Further description / examples of skin changes	Numbness, dysesthesia / paresthesia tingling, painless swelling, or erythema of the hands and/or feet	Painful erythema and swelling of the hands and/or feet	Moist desquamation, ulceration, blistering, or severe pain of the hands and/or feet
Effect on activities	Does not disrupt normal activities	Limiting instrumental activities of daily life (e.g., preparing meals, shopping for groceries or clothes, using the telephone, managing money)	Limiting self-care activities of daily life (e.g., bathing, dressing and undressing, feeding self, using the toilet, taking medications) and not bedridden
a. Palmer-planter erythrodysesthesia syndrome is a disorder characterized by redness, marked discomfort, swelling, and tingling in the palms of hands or the soles of the feet.			

Table 4: Recommended Dose Modification for Hand-Foot-Skin Reaction^a

CTCAE v 4.0 Grade	Occurrence	Suggested Dose Modification
Grade 1	Any	Maintain dose level and immediately institute supportive measures for symptomatic relief
Grade 2	1 st occurrence	Tolerable Grade 2: No change In-tolerable Grade 2: Decrease dose by one dose level and immediately institute supportive measures. If no improvement, interrupt therapy for a minimum of 7 days, until toxicity resolves to Grade 0-1 ^{b, c}
	No improvement within 7 days or 2 nd occurrence	Interrupt therapy until toxicity resolves to Grade 0-1. ^c When resuming treatment, treat at reduced dose level ^b
	3 rd occurrence	Interrupt therapy until toxicity resolves to Grade 0-1. ^c When resuming treatment, decrease dose by one dose level. ^{b, d}
	4 th occurrence	Discontinue therapy
Grade 3	1 st occurrence	Institute supportive measures immediately. Interrupt therapy for a minimum of 7 days until toxicity resolves to Grade 0-1. ^c When resuming treatment, decrease dose by one dose level. ^{b, d}
	2 nd occurrence	Institute supportive measures immediately. Interrupt therapy for a minimum of 7 days until toxicity resolves to Grade 0-1. ^c When resuming treatment, decrease dose by one additional dose level ^{b, d}
	3 rd occurrence	Discontinue treatment permanently.

- a. More conservative management is allowed if judged medically appropriate by the investigator.
- b. If toxicity returns to Grade 0-1 after dose reduction, dose re-escalation is permitted at the discretion of the investigator if subject has completed one cycle at reduced dose without recurrence of event.
- c. If there is no recovery after a 4-week delay, treatment with regorafenib will be discontinued permanently.
- d. Subjects requiring > 2 dose reductions should go off protocol therapy.

